2.5. Secondary analyses

Purpose:

1. To evaluate interactions of treatments in the change of BP over 12 months.
2. To evaluate the pattern of change of BP over time.
3. To evaluate time from ED visit to arrival at first primary care visit (in days).
4. To evaluate attendance at two or more primary care visits within 12 months of randomization.

Methods/Approach: The following secondary analyses will be presented:

(a) Other analysis approaches on the primary measurement:

Additional analyses will include all the two-way interactions of the three intervention components (only considering interactions where at least one of the factors in the interaction demonstrates a sufficiently large main effect) added to the primary model in Section 2.4. Interactions between treatments will be assessed at $p=0.2$.

Since BP levels are captured at least weekly, we will also model BP (captured by text and in person visits) over time using a mixed effects model to see the pattern of blood pressure levels over time. The outcome of this longitudinal model will be BP levels over time (transformed if necessary), where the number of BP levels per person can vary. The fixed effects of the model include: the 3 main effects binary coded treatment predictors and the 3 stratification variables as specified in the primary analysis model. A random slope for a continuous time variable measured in days from randomization and a random intercept to allow subject specific heterogeneity in baseline BP and BP trajectories over time. We will assume compound symmetry for the covariance matrix but assess the appropriateness of this assumption using AIC and BIC compared to unstructured and autoregressive structures. We will also assess the significance of two-way interactions of treatments (only where at least one of the factors demonstrates a sufficiently large main effect) in this model at the 0.2 level. Mixed effects models are robust to data missing at random.

As a sensitivity analysis, similar to a per protocol analysis, we will assess the effect of using group variables that may change from week to week as opposed to the given randomized treatment variable that stays fixed over the treatment period (intent to treat group). For example, if someone de-escalates from daily to weekly monitoring in a particular week, we can capture this in a longitudinal model by allowing their group variable to change from daily to weekly in that week. This will allow us to connect the BP measurement with the group assignment for that week, thus we will use all BP measurements. Otherwise, the mixed model construction will be the same as detailed in the paragraph above.

(b) Other outcomes (secondary outcomes):

- To evaluate time from ED visit to arrival at first primary care visit (in days)

- Unadjusted survival distributions for receiving provider scheduling and transportation versus not and for all 8 intervention arms will be estimated and plotted by the Kaplan-Meier method and compared using the log-rank test.
- Cox proportional hazards regression model will assess the time from ED visit to arrival at the first primary care visit where all of those who do not have a recorded PCP visit will be censored at the time of last follow-up (last communication/text) or 12 months. The main predictor of interest for these models is assignment to the active primary care provider scheduling and transportation arm (50% of all subjects randomized in the trial), while adjusting for the assignment into other groups (healthy behavior text messages and prompted BP self-monitoring). We will control for age, sex, previous use of antihypertensives, and race. The interactions of these baseline variables will be assessed. The proportionality assumption will be assessed via Schoenfeld residuals by evidence of a non-zero slope in a generalized linear regression of the scaled residuals by time and goodness of fit will be assessed by the Grambsch-Therneau test.
- To evaluate attendance at two or more primary care visits within 12 months of randomization.
 - This binary endpoint will be assessed using logistic regression. The main predictor of interest for these models is assignment to the active primary care provider scheduling and transportation arm (50% of all subjects randomized in the trial), while adjusting for the assignment into other groups (healthy behavior text messages and prompted BP self-monitoring). We will control for age, sex, previous use of antihypertensives, and race. The interactions of these baseline variables will be assessed. Hosmer-Lemeshow Chi-Squared test will assess the goodness of fit.

(c) Since the goal of this exploratory trial is to find interventions and combinations with activity, multiple comparisons will not be controlled.

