We will conduct additional exploratory analyses using the stratification factors (age, sex, and antihypertensive use) as covariates. As uncertainty exists on the distribution of enrolled participants within these strata (e.g. young men taking antihypertensive medication), we cannot estimate the preliminary statistical power for these exploratory aims. Thus, we will estimate the power based on the strata sizes prior to conducting the exploratory analyses. Interaction terms (e.g. age with behavioral interventions, sex with behavioral interventions, etc.) will be utilized to determine if specific groups respond well to specific intervention elements. Baseline BP may also play an important role. We will examine its impact by dividing the cohort into tertiles. We will repeat the above primary and exploratory modeling within each of the three initial BP strata to determine if there is heterogeneity of effect (e.g. do patients with the highest baseline BPs get the most benefit from the intervention components?). We will similarly assess the impact of the intervention components on the exploratory and process outcomes using linear, Poisson, logistic, or ordinal regression depending on the distributions. In addition, we will conduct longitudinal analyses that include all BP measurements over time (including those by text and at the in-person visits) to assess the temporal profiles of response in the intervention components.

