2.6 Subgroup analyses

Purpose: To evaluate the heterogeneity of treatment effects by baseline characteristics of age, sex, previous antihypertensive medication, race, and baseline BP level.

Methods/Approach:

- To assess the heterogeneity of treatment effects by age, sex, previous antihypertensive medication and race, the two-way interactions of the main effects of treatments and these covariates will be assessed at the 0.2 significance level
- To assess the heterogeneity of treatment effects by baseline BP, we will divide the cohort into tertiles based on their initial BP level (median of three qualifying SBP from eligibility phase). We will repeat the above primary (Section 2.4) and secondary modeling (Section 2.5a) within each of the three initial BP strata to determine if there is heterogeneity of effect (e.g. do patients with the highest baseline BPs get the most benefit from the intervention components?).

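### The longitudinal BP model in SAP 2.5(a) has no component-by-time terms, so it cannot show how each component's effect develops over the year

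*SAP*

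**What the plan says.** Protocol 9.1 promises longitudinal analyses of all BP measurements, texted and in person, "to assess the temporal profiles of response in the intervention components". SAP 2.5 gives the second purpose of its secondary analyses as "To evaluate the pattern of change of BP over time", and SAP 4 lists a table on that pattern from baseline to month 12.

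The model is in SAP 2.5(a). Its outcome is the BP level at each reading, "where the number of BP levels per person can vary". On the mean structure it says: "The fixed effects of the model include: the 3 main effects binary coded treatment predictors and the 3 stratification variables as specified". The specification it points to is the regression of SAP 2.4. Time appears in one place: "A random slope for a continuous time variable measured in days from randomization and a random intercept". The only interactions named are two-way interactions between treatments. On covariance it says: "We will assume compound symmetry for the covariance matrix but assess the appropriateness of this assumption using AIC and BIC". The alternatives to be tried are unstructured and autoregressive.

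The same model is used twice more. For the sensitivity analysis in which group can change week by week, "Otherwise, the mixed model construction will be the same as detailed in the paragraph above". For the baseline-BP tertiles, SAP 2.6 says: "We will repeat the above primary (Section 2.4) and secondary modeling (Section 2.5a) within each of the three initial BP strata".

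SAP 2.4 also plans plots of mean BP over time by component and by arm.

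**The concern.** A model meant to show how response develops over the year needs a term that lets each component's effect vary with time. None is named in SAP 2.5(a), 2.6 or 4. A random slope lets individuals depart from the mean trajectory, but it does not give the two levels of a component different mean trajectories.

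Two things are at stake. First, a stated purpose of the SAP is not met by the model written for it. Second, the coefficient that is reported has no fixed meaning when an effect grows, plateaus or fades. It need not equal the 12-month effect or the simple average over the year, and it can move with a covariance choice that the SAP leaves to AIC and BIC. Reading frequency also affects the weights, and daily versus weekly prompting is itself one of the randomised components (protocol 6.1.2).

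**Working it through.** The documents give no figure for this model, so there is none to reproduce.

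**Step 1: what the model can express.** The random effects have mean zero, so the model as written gives

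E[BP(t)] = b0 + b1·HBtexts + b2·HighBPmonitor + b3·PCPfacilitated + stratification terms.

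The right-hand side contains no t. The difference between the two levels of the text component is b1 on day 1 and on day 365, and likewise b2 and b3 for the other two. Treatment-by-treatment terms change that constant by arm, not over time. A common fixed time term cancels from the difference. This step needs no assumption.

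**Step 2: what the constant estimates when the true effect is f(t).** By generalised least squares with V = ZGZ' + s²I, where Z holds the intercept and time columns, G is the random-effect covariance and s the residual SD:

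coefficient = Σ(1'V⁻¹f) / Σ(1'V⁻¹1).

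If f is constant the ratio is 1, so an immediate, stable effect is recovered in full.

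Assumed inputs, none of them from the documents: intercept SD 12 or 15 mm Hg; slope SD 5, 8 or 12 mm Hg per year; residual SD 8, 10 or 12 mm Hg; intercept-slope correlation -0.5, -0.3, 0 or +0.3; 52 complete weekly readings. The shapes are f = t/52, min(t/8, 1) and min(t/13, 1), with t in weeks, and a triangle peaking at week 26 and zero at week 52.

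Simple time-averages for comparison: linear 53/104 = 51%; 8-week build-up (4.5 + 44)/52 = 93%; 13-week build-up (7 + 39)/52 = 88%.

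Coefficient as a share of the 12-month effect:

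| Correlation | Linear growth | 8-week build-up | 13-week build-up |
|---|---|---|---|
| -0.5 | 50 to 113% | 93 to 116% | 88 to 125% |
| -0.3 | 32 to 75% | 86 to 102% | 77 to 103% |
| 0 | 5 to 29% | 76 to 85% | 62 to 76% |
| +0.3 | -38 to -2% | 61 to 74% | 37 to 58% |

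The mid-year peak, truly zero at 12 months, appears as a constant 46-55% of its peak.

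With half the participants prompted daily and half weekly, and 47% of prompts answered, the ranges over the grid are -41% to 115%, 56-119% and 32-128% for the three growing shapes. The 47% is the response to weekly prompts in the church pilot (protocol 2.2.1); using it for daily prompts is a further assumption.

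**Step 3: sensitivity to the covariance structure.** Take SDs of 13 (intercept), 8 (slope) and 10 (residual), weekly readings and linear growth. At correlation 0 the coefficient is 14% of the 12-month effect with independent residuals and 20-38% with AR(1) residuals at autocorrelation 0.3 to 0.9. At correlation -0.3 it hardly moves, at 49-50%. With a random intercept only it is close to the time-average (50-51%, 93% and 88% for the three growing shapes).

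**Step 4: simulation.** Maximum likelihood, 240 people on the mixed schedule, the same SDs, common trend -6 mm Hg per year, text effect growing linearly to -4 mm Hg at 12 months (time-average -2.0), 60 trials per correlation. The model as written gave mean coefficients of -3.2, -1.9, -0.7 and +1.1 mm Hg at correlations -0.5, -0.3, 0 and +0.3 (Monte Carlo SE 0.18-0.24). Adding fixed time alone changed no mean by more than 0.04.

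**Step 5: which time form repairs it.** With a component-by-time basis C, the fitted profile is C(ΣC'V⁻¹C)⁻¹ΣC'V⁻¹f, read at week 52. Ranges cover the grid and both schedules:

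| Form | 8- and 13-week build-ups, % of 12-month effect | Mid-year peak, % of peak (truth 0) | SE relative to the constant coefficient |
|---|---|---|---|
| Linear interaction | 111-119% | 47-50% | 1.00-1.64 |
| Spline, interior knots at weeks 13, 26, 39 | 97-100% | 2% | 1.02-1.67 |
| Four-week intervals | 84-101% | 6-7% | 1.02-1.62 |

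The last four-week interval averages weeks 49-52, so it does not read exactly at week 52. For linear growth the linear interaction is exact.

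**The case against.** The strongest reply is about scale. Protocol 9.1 introduces this work as exploratory and the SAP treats it as secondary; the primary endpoint and selection rule do not use it. The plots in SAP 2.4 will show mean BP over time by component. The SAP says the fixed effects include the listed terms, which does not strictly exclude others, and its reference to individual trajectories may presuppose a mean time trend. The percentages rest on assumed variances and shapes: negative values occur only at correlation +0.3 with growth all year, and at -0.3 the 8-week build-up is recovered at 86-102%. The 12-month effect is the target of the primary regression, not obviously of this model. Finally, 16 extra parameters are heavy in tertiles of about 240/3 = 80 completers, and in the week-by-week model time since randomization has no clear meaning after a switch.

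Much of this stands as a limit on size. The status is secondary, the percentages are conditional, and the plots reduce the loss to model-based differences and their intervals. None of it supplies the missing term. A presumed fixed time trend cancels from the component difference, and a term added after seeing the data would not be pre-specified. The points about the tertile and week-by-week models bear on how the fix is applied there.

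**Conclusion.** The concern holds. As written, the model gives one constant difference per component and cannot meet the second purpose of SAP 2.5 or the aim in protocol 9.1. Confidence is high for that structural point, which needs no assumption.

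The numerical consequence is conditional on variances and effect shapes that the documents do not give. It runs from none (a constant effect, or near-full recovery at some negative correlations) to a coefficient of the wrong sign (linear growth at correlation +0.3). The size was not computed for the week-by-week sensitivity model or the tertile models. The change should be made, but it does not threaten the trial's main conclusion.

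**What to change.** In SAP 2.5(a), add fixed time in a flexible or categorical form, for example a natural cubic spline or monthly intervals, and its interaction with each of the three components. Report each component's BP difference over time and at 12 months with confidence intervals. Do not rely on a linear interaction alone, because it misstates effects that plateau or fade. The knots at weeks 13, 26 and 39 are one workable choice, not the only one; whichever form is chosen should be fixed before the data are examined.

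Carry the same mean structure into the week-by-week sensitivity model and the tertile models. For the former, state what the time interaction means after a participant switches group. For the latter, expect wide intervals given the small strata.

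The cost is SAP wording; no new data are needed. The three-knot spline adds 16 parameters (4 time terms and 3 × 4 = 12 interactions). Under the assumed variances, the standard error of the 12-month difference is 1.02 to 1.67 times that of the constant coefficient.

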Appendix E – Flyer for Text Message Instructions

Instructions for Text Messages

You will be getting text message reminders to take your blood pressure (BP).

To make sure you are able to receive and send messages:

- 1 When you get the text from REACH OUT to take your BP, follow the instruction sheet for taking your BP at home
- 2 Text your BP to "REACH OUT" as xxx/xxx (for example: 135/80)

If you want to know all the changes you can make to your text messages, just text 'HELP'

You can take a break from getting text messages. Just text 'SNOOZE'

- After a 2-week break, you will start getting text messages again.

You can change how often you get text messages to remind you to take your BP.

- Text 'DAILY' to get text message reminders every day.
- Text 'WEEKLY' to get text message reminders once a week.

If you would like us to send a graph that tracks your BP readings, text 'GRAPH'

You can stop participating in the REACH OUT project at any time. Just text 'END'

Things to know before you decide to 'END':

- You won't receive any more text message reminders to take your blood pressure.
- We'll only contact you for follow-up at 6 months and 12 months.

Important: The text messages are not read by medical providers, so never text medical questions. If you are having an emergency, please call 911

Abbreviations we may use:
BP = Blood Pressure
ED = Emergency Department
Dr = Doctor
Meds = medications

REACH OUT
For Lower Blood Pressure

Have questions about REACH OUT study? Call or text the REACH OUT staff at [contact]

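### SAP 2.5(a) pairs each BP with the dose the participant chose that same week, so if BP prompts switching, that can show up as a dose effect; treat the result as a descriptive as-treated analysis

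*SAP*

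**What the plan says.** SAP 2.5(a) introduces the analysis with "As a sensitivity analysis, similar to a per protocol analysis" and continues: "we will assess the effect of using group variables that may change from week to week as opposed to the given randomized treatment variable". The randomised variable gives way to a group that follows what the participant is actually receiving. The SAP's example is a participant who moves from daily to weekly, handled by "allowing their group variable to change from daily to weekly in that week". The stated purpose is: "This will allow us to connect the BP measurement with the group assignment for that week, thus we will use all BP measurements". Then: "Otherwise, the mixed model construction will be the same as detailed in the paragraph above".

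That earlier paragraph sets out the model. "The fixed effects of the model include: the 3 main effects binary coded treatment predictors and the 3 stratification variables", with a random intercept and a random slope for time. Compound symmetry is the starting covariance, to be compared with unstructured and autoregressive forms by AIC and BIC. It lists no earlier BP, lag, weighting, model for switching or fixed effect for time.

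The participant controls the exposure. Protocol 6.1.2 lets participants reset their own reminder frequency, and Appendix E gives the commands: "Text 'DAILY' to get text message reminders every day" and "You can take a break from getting text messages. Just text 'SNOOZE". They read their own cuff and receive a monthly graph. SAP 2.3 adds that the weekly command also stops healthy behavior texts, so one choice can move two components at once.

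**The concern.** A per-protocol analysis is meant to show what happens when people stay on what they were assigned. This one compares weeks on a dose that people chose, with nothing in the model to separate BP changing the dose from dose changing the BP. If someone sees a high reading and asks for daily reminders, and that reading is then filed under daily, daily prompting looks harmful even when it does nothing. A random intercept removes stable differences between people, but not this week-to-week feedback within a person.

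What is at stake is interpretation. SAP 2.3 and the compliance table in SAP section 4 only count snoozes and switches, so this is the only model of received dose. It would be read beside the intention-to-treat estimate, and any agreement or disagreement could be taken as evidence about adherence. SAP 2.6 also repeats the 2.5(a) modelling within tertiles of baseline BP.

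**Working it through.** SAP 2.5(a) gives no figure for this analysis, so there is none to reproduce. The only plan value used for scale is the minimum effect per component of 1 mm Hg (Protocol 9.3).

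**Model.** Write y(i,t) = a(i) + s(i)·t + e(i,t), with a true dose effect of zero. Any average coefficient for daily minus weekly is then bias.
- If the dose filed against week t depends on y(t), the mean of e(t) differs between daily and weekly weeks. No choice of covariance removes that.
- If the dose in week t depends only on the texted y(t−1), the link runs through the correlation of e(t) with e(t−1). A correctly specified autoregressive model accounts for it.

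**Inputs.** From the plan: N = 240 (anticipated completers) and two-sided alpha 0.10. Assumed, not in the documents: 52 weekly BPs each; between-person SD 12, slope SD 8 per year and within-person SD 10 mm Hg; log-odds of moving to daily up, and to weekly down, by 0.7 per 10 mm Hg (odds ratio e^0.7 ≈ 2.0). There were 120 simulated trials per setting, rejecting when |estimate/SE| > 1.645. The Monte Carlo SE of the mean estimates below is 0.03 to 0.07.

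| Switch prompted by | True / fitted errors | Weeks off assigned dose | Mean estimate (mm Hg) | p < 0.10 |
|---|---|---|---|---|
| Same week's BP | independent / independent | 39% | +2.07 | 100% |
| Same week's BP | autocorrelation 0.5 / AR(1) | 39% | +3.37 | 100% |
| Same week's BP | autocorrelation 0.5 / AR(1) | 15% | +2.22 | 97% |
| Last week's BP | autocorrelation 0.5 / independent | 39% | +0.80 | 79% |
| Last week's BP | autocorrelation 0.5 / independent | 15% | −0.03 | 27% |
| Last week's BP | independent / independent | 39% | +0.02 | 13% |
| Last week's BP | autocorrelation 0.5 / AR(1) | 39% | +0.04 | 8% |
| Unrelated to BP; BP falls 8 mm Hg over the year; no fixed time term | autocorrelation 0.5 / independent | 31% | +0.46 | 41% |

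The randomised comparison on the same data had mean 0.09 to 0.10 and rejected in 11–12%. With 120 trials the Monte Carlo SE of a 10% rate is √(0.10 × 0.90 / 120) = 0.027, so 8% to 13% is compatible with 10%.

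A separate simulation of 25 runs per setting gave +2.7 to +4.1 mm Hg with 100% rejection under same-week coding, and about zero with 8% rejection when dose was fixed before the reading and errors were AR(1). Together, same-week coding gives about 2 to 4 mm Hg, or 2 to 4 times the 1 mm Hg minimum.

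In the last row of the table, autocorrelation was also left unmodelled, so the 41% is not due to the missing time term alone. No adequately sized run isolates that term. The reason to add it is that a BP trend and a drift in the dose mix are otherwise confounded.

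**The case against.** **The covariance check helps.** The SAP does not commit to independent errors. In 500 runs per setting with switching prompted by the previous week's BP (5–10% weekly chance of moving to daily above 150 and to weekly below 135; autocorrelation 0.3–0.6), a random intercept and slope with independent errors gave bias of +0.09 to +0.88 mm Hg and 20–73% rejection. Adding AR(1) brought bias within about 0.03 of zero and rejection to 10–13%, and AIC chose AR(1) every time. This stands: for switching driven only by earlier texted readings, the SAP's own check largely solves the problem. It does not help when the prompting BP is filed under the new dose, where AR(1) still gave +3.37. Nor does it cover untexted readings (Appendix A asks for four readings a day and a reply with the first) or a medication change.

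**The coding is not fully specified.** The SAP does not settle whether a BP texted earlier in the week than the switch command takes the old or the new dose. That is true, and it is a reason to state the rule.

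**Switching may have nothing to do with BP.** Message fatigue is as plausible, and people with high BP who drop to weekly would reverse the sign. This stands, so a reader who infers a demonstrated bias, or a bias that makes daily monitoring look harmful, goes further than the documents allow.

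**The stakes are limited.** A reader might infer that this analysis could steer the choice of dose for the next trial. The documents do not support that. The dose in the aims is the randomised level, and the selection rule (Protocol 9.1; SAP section 1) rests on main-effect and interaction tests at 0.10 and 0.20.

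**Conclusion.** The point holds as an uncontrolled risk in one sensitivity analysis. As described, it is an as-treated comparison on a self-chosen exposure and cannot do the job of a per-protocol check. The 2 to 4 mm Hg false effect rests on assumed variances, switching strongly tied to BP, and the prompting BP being filed under the new dose. With dose fixed before the reading, switching driven only by texted BP and the covariance right, the error is about zero. The primary analysis in SAP 2.4 keeps everyone as randomised and is untouched. It would be wrong to conclude that any week-by-week dose model is invalid, or that this one must be replaced by an instrumental-variable analysis. This is a cheap improvement.

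**What to change.** 1. Pair each BP with the dose in force before that reading, so that a BP sent before a switch command keeps the old dose. Add a fixed effect for time, and retain an autoregressive covariance if AIC/BIC favours it. State how snoozed and ended weeks are coded.
2. Call the result descriptive as-treated, drop the per-protocol comparison, and state that it does not inform component selection. The label is still needed after step 1, because lagging does not deal with untexted readings or other unmeasured reasons for switching.
3. Optionally, if an adherence estimand is wanted, add (do not substitute) one of the following:
   - A complier average causal effect on 12-month SBP change, with the randomised monitoring and text levels as instruments for the two logged doses. State the exclusion and monotonicity assumptions, and code weekly prompting separately from snoozed or ended weeks so that it is not merged with no prompting. This largely rescales the intention-to-treat estimate and is not an independent test.
   - Inverse-probability weighting on BP history.

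Cost: a revised SAP paragraph and a little more analysis. The switching records are already needed for the counts in SAP 2.3. The complier estimate would have a wider interval.
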